#### 7.1.4 Missing Data Analyses

Every effort will be made to avoid missing data. Still, we plan to enroll 64 subjects per arm to achieve 51 completed subjects, as described in the Sample Size Justification. For missing data, we will explore the missing data mechanism whether it is missing completely at random, missing at random, or missing not at random. We will test whether missingness on the primary endpoint depends on covariates and whether the missing data mechanism is ignorable. After a good understanding about the missing data mechanism, we will adopt two strategies to deal with missing data. The multiple imputation method that incorporates predictive mean matching and flexible additive imputation models as implemented in the *aregImpute* function in the Hmisc package (Harrell, 2013, page 12) in R will be used. We will also conservatively impute missing data to perform sensitivity analyses. Imputing strategies could be last-value-carry-forward (we believe this imputation is conservative since subjects on placebo may get worse and subjects on CLEAR may get better if they stayed in the study, and we assume a flat carry-forward) or we could assume a spontaneous improvement rate for the placebo arm estimated from the non-missing data if that is observed. The primary analysis is the intention-to-treat (ITT) analysis of the complete data set. These additional analyses that deal with missing data are secondary and they are to corroborate study findings from the primary ITT analysis.

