#### 7.1.2 Approaches to the Analysis

The following 2 approaches will be used for the analyses:

- **Intention-to-Treat** All patients with a post-treatment endpoint measurement will be included. This will be considered the primary analysis and performed for all endpoints.
- **Per Protocol** This will be performed as a secondary analysis for the primary endpoint only. A patient who is identified as a major protocol violator will not be included. Protocol violators will be considered as follows: 1) Realize that patient did not meet Inclusion Criteria after enrolled into study; 2) Find an Exclusion criteria after enrolled into the study; 3) Regimen was

permanently stopped before 4 weeks; 4) Exacerbation requiring greater than 2 weeks of prednisone escalation. Major protocol violators will also be defined based on criteria that will be identified prior to unblinding the database.

**7.1.3 Multiplicity:** Since there is only 1 primary comparison for 1 primary endpoint for each study aim, and other comparisons are secondary and supportive, no multiplicity adjustment will be applied.

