### 7.3 Sample Size Justification

Sample size is calculated for primary endpoint; change from baseline of FVC percent predicted. Using data from 34 participants treated with Bosentan to treat pulmonary hypertension, we obtained the SD of 7.7 for the primary endpoint. We need a sample size of 51 completed participants per arm to have 90% power to detect a 5% difference (5% in CLEAR vs. 0% in placebo) in change of FVC percent predicted from baseline. To factor in a 20% dropout rate, we plan to enroll 64 subjects per arm. This brings the sample size to 128 participants. In the Phase I trial, we experienced a higher drop rate 30%, but review of the clinical data demonstrates that patients with advanced disease accounted for the majority of the study withdrawals. The Phase II trial will allow patients to drop one study drug, and will include a research nurse coordinator to encourage study participation. We anticipate that we will have not have as high a study withdrawal rate.

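### Section 7.1.4 plans to test whether missing week 16 FVC is ignorable, which observed data cannot show, and no planned sensitivity analysis explicitly shifts missing CLEAR values downward

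*Combined protocol and SAP*

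**What the plan says.** Section 7.1.4 (Missing Data Analyses) intends to establish whether missing values are MCAR, MAR or MNAR: "We will test whether missingness on the primary endpoint depends on covariates and whether the missing data mechanism is ignorable". It names no test, model, covariate list or significance level. It continues: "After a good understanding about the missing data mechanism, we will adopt two strategies to deal with missing data".

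The first strategy is multiple imputation with aregImpute. The second is a conservative imputation. For this, "Imputing strategies could be last-value-carry-forward", which is judged conservative because placebo patients might have worsened and CLEAR patients improved had they stayed. Alternatively, "we could assume a spontaneous improvement rate for the placebo arm estimated from the non-missing data if that is observed".

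On the status of this work: "These additional analyses that deal with missing data are secondary and they are to corroborate study findings from the primary ITT analysis". The primary analysis that it supports is defined in section 7.1.2: "All patients with a post-treatment endpoint measurement will be included".

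Section 7.3 plans for 20% dropout. It also reports 30% in Phase I, mostly among patients with advanced disease.

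**The concern.** Ignorability turns on whether, given everything recorded, the chance of a missing week 16 FVC still depends on that unseen value. Two mechanisms, one MAR and one MNAR, can fit the recorded data equally well, so no test on those data separates them without assumptions that are themselves untestable. What can be tested is dependence on observed covariates and on week 4 and week 8 FVC. That is a check of MCAR and says nothing about the step from MAR to MNAR.

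This matters because of what surrounds the test. The primary comparison uses measured patients, and multiple imputation as described relies on MAR. Carry-forward is not a MAR method, but its claim to be conservative presumes that CLEAR patients would have improved, which is the effect under study. The placebo-rate option leaves the missing CLEAR values alone. Nothing listed asks how much worse the missing CLEAR patients would have to be before the conclusion changes. Agreement among these analyses could therefore be read as stronger support than it is.

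**Working it through.** **1. The plan's own figures.** Section 7.3 states "we obtained the SD of 7.7 for the primary endpoint" and "We need a sample size of 51 completed participants per arm to have 90% power to detect a 5% difference". Alpha is not stated; two-sided 5% is assumed.
- Normal approximation: n = 2 x (1.96 + 1.2816)² x 7.7² / 5² = 49.8, so 50 per arm. The noncentral t gives 50.8, so 51, with 90.1% power. The plan's figure is reproduced. One-sided 5% would give only 41.
- Enrolment: 51 / 0.80 = 63.75, so 64 per arm and 128 in total. Expected missing: 128 - 102 = 26.

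**2. General size of the bias.** Let a fraction 0.20 of CLEAR be missing, with mean change D points below the measured CLEAR mean, and let placebo dropout be uninformative. The mean over all CLEAR patients is 0.80 x m + 0.20 x (m - D) = m - 0.20 x D, where m is the measured mean. The measured-patient difference is therefore too high by 0.20 x D.

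| D (points) | Bias at 20% missing | Bias at 30% missing (Phase I rate) |
|---|---|---|
| 2.5 | 0.5 | 0.75 |
| 5 | 1.0 | 1.5 |
| 7.7 | 1.54 | 2.31 |
| 10 | 2.0 | 3.0 |

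**3. What the planned analyses would leave.** Simulation inputs from the plan: 64 per arm, SD 7.7, 20% missing. Assumed inputs: no true effect, random placebo dropout, and CLEAR dropout odds rising e-fold per SD of worse week 16 change. There were 3,000 trials per setting. MAR imputation is represented by per-arm regression on week 8 change, not by aregImpute itself. Bias in points:

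| Week 8/week 16 correlation | Measured only | MAR imputation | Week 8 carried forward |
|---|---|---|---|
| 0 | +1.37 | +1.37 | about +1.1 (0.80 x 1.37) |
| 0.3 | +1.33 | +1.22 | +0.74 |
| 0.5 | +1.30 | +0.98 | +0.49 |
| 0.7 | +1.33 | +0.71 | +0.31 |

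Carrying the baseline forward instead leaves +1.04 to +1.07 at correlations 0.3 to 0.7. With half the log-odds slope (0.5 per SD), the measured-patient bias is +0.73 to +0.77, MAR imputation leaves +0.37 to +0.71, and week 8 carry-forward +0.17 to +0.45.

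**4. The same mechanism in both arms.** Bias is about 0 (-0.03 to +0.04).

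**5. Whether a test result tracks the bias.** At correlation 0.7 and the strong slope, a pooled t-test of the week 8 covariate (missing against observed) is significant in 80% of trials when both arms are informative and the bias is nil. It is significant in 27% when only CLEAR is informative and the bias is +1.3. At correlation 0 it fires at about 5%, which is alpha. Significance is thus a poor guide to bias in the arm difference.

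**6. What a tipping-point analysis could show.** With 51 per arm the standard error is 7.7 x √(2/51) = 1.525, so a difference of about 1.984 x 1.525 = 3.0 points is just significant. Ignoring the extra imputation variance, an estimated difference of 4 tips at a shift of about (4 - 3.0) / 0.20 = 5 points, and a difference of 5 at about 10 points.

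**The case against.** The strongest reply is that the test controls nothing. Section 7.1.4 gives no threshold and no branch. Multiple imputation and conservative imputation are both planned whatever the test shows, and the corroborating role is given to them, not to the test. That is correct. A reader might infer that a non-significant result would certify the primary finding, but the documents contain no such rule.

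A reader might also infer that 26 missing values are too few for the test. For ignorability the number is irrelevant. Power concerns only the covariate check, which is legitimate and not hopeless: with 26 against 102 it has 62% power at a 0.5-SD difference and 80% at 0.62 SD. A test confined to CLEAR also does better than a pooled one when only CLEAR dropout is informative, at about 15%, 30% and 52% for correlations of 0.3, 0.5 and 0.7.

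It is also too strong to say that every planned analysis repeats the error. Carry-forward keeps any decline already seen, and in the simulation it removed a material part of the bias. Crediting missing placebo patients with improvement would work against CLEAR. Neither is a controlled departure from MAR for missing CLEAR patients.

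Finally, the plan limits missingness. Sections 5.1 and 7.2 continue follow-up after drug is stopped, section 5.7 asks those who stop for at least spirometry, and section 7.1.1 accepts values from weeks 12 to 20. These steps may reduce the number missing. They do not make the mechanism testable.

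**Conclusion.** The point stands in a limited form. The plan promises a test that cannot be carried out as described, and it lacks an analysis that varies the MAR assumption against CLEAR. The claim that carry-forward is conservative is not supported, since it errs in CLEAR's favour in every CLEAR-only setting shown.

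The figures are illustrations, not forecasts. The +1.3 points is about a quarter of the 5-point target, and in those settings the two-sided error of the measured-patient t-test is about 15% instead of 5% (7% to 8% with the weaker slope). Both rest on dropout being informative in CLEAR alone, at strengths and correlations the documents do not give. A reader might infer that the trial's result will be biased. The documents do not support that: the Phase I withdrawals suggest dropout may relate to severity, but nothing shows that it would differ by arm. The primary test and sample size are unaffected. The change should be made because it settles how robust a positive result is.

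**What to change.** In section 7.1.4 (Missing Data Analyses):

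- Replace the ignorability test, and the plan to establish the mechanism first, with a descriptive comparison of missingness by arm, covariates and week 4 and week 8 FVC.
- State that MAR is an untestable working assumption, and keep the aregImpute analysis under it.
- Remove the statement that carry-forward is conservative.
- Prespecify a delta-adjusted (tipping-point) analysis. Shift the imputed week 16 changes of missing CLEAR patients down in 1-point steps, for example 0 to -8 (about one SD), with placebo unshifted. Report the shift at which significance is lost, or that it is not lost within the range, and judge it against the observed spread of change.

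The cost is some SAP wording and a short loop around imputation already planned, with no new patients or data. The downside is a little more analysis and a sensitivity result that may look less reassuring.

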## 7. Statistical Considerations

### 7.1 Statistical Methods

#### 7.1.1 Analysis of Primary Endpoint

The comparison between CLEAR and placebo arms will be made using the Students's t-test. Normality of the primary endpoint will be examined using Kolmogorov-Smirnov test. If normality is violated, the comparison between CLEAR and placebo arms will be made using the Wilcoxon rank sum test.

The primary endpoint of this study is the arithmetic difference between %FVC predicted value measured at baseline and week 16 for each patient randomized. For analysis purposes, we define the week 16 post-randomization %FVC predicted value measurement at the value closest to 16 weeks from randomization within a window of 12 weeks to 20 weeks from randomization. This more accurately represents the data collected at 16 weeks on study due to the variability of visit schedules resulting from staggering the start of study drugs and patient scheduling. To understand the trajectory of improvement with CLEAR therapy, we will also be measuring the %FVC predicted value at weeks 4 and 8. If the improvement is linear in time, the rate of improvement (slope of change) may be reported as a secondary endpoint in the study.

This analysis is an exploratory analysis. Mixed effect models will be used to analyze these repeated measures with a random subject effect and with the treatment (CLEAR versus placebo) and the time trend (baseline, week 4, week 8, and week 16) as fixed effects. For the error covariance, we will use autoregressive model of order 1 [AR(1)] or other plausible covariance structures. The focus of this study will be the treatment effect and the time trend of the endpoint; however, mixed effect models also provide the flexibility of controlling for and evaluating covariates such age, race, and gender.

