## 7.2 Randomization

Participants will be randomized to either CLEAR therapy or placebo at a ratio of 1 to 1 stratifying by site and use of prednisone  $\geq 10$  mg or not and using a permuted-block randomization algorithm with random block sizes. Treatment assignments of the study will be made using separate randomization schedules for each of the three participating sites. The randomization schedule will be prepared by the DCC prior to initiation of patient recruitment. Randomization schedules will be generated by a statistician who is not involved with the conduct of the clinical trial. All randomization schedules will be generated using R, will remain confidential and known only by the site pharmacists until the database is locked and randomization assignments no longer must be blinded. Randomization marks the patient's official entry into the Study. Once a participant has been started on the assigned study treatment, efforts will be made to conduct all evaluations irrespective of whether the participants complete the study treatment regimen or not, or how well the participants complies with the study treatment regimen. These efforts should continue until termination of the study. Data collections will continue even if medication must be stopped.

For the intention to treat analysis, participants will be considered treated when the first study drug is taken, regardless of the amount of study drug they receive. Participants discontinued from receipt of

study drug for any reason, will continue to follow all other protocol requirements for the entire study period to the extent that the informed consent is still active.

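### LOCF is called conservative, but this is not guaranteed: it can overstate the week 16 effect in all randomised patients while looking cautious next to the completers' estimate

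*Combined protocol and SAP*

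**What the plan says.** Section 7.1.4 Missing Data Analyses first proposes to study the missing-data mechanism: "We will test whether missingness on the primary endpoint depends on covariates and whether the missing data mechanism is ignorable". It then commits to two strategies. Multiple imputation (aregImpute) will be used, and a deliberately conservative imputation will serve as a sensitivity analysis. LOCF is one option for the second, on the ground that "we believe this imputation is conservative since subjects on placebo may get worse and subjects on CLEAR may get better if they stayed". The other option is a spontaneous improvement rate for placebo, estimated from the observed data. All of this is secondary and meant to corroborate the primary analysis of the complete data set.

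Section 7.1.1 defines the primary endpoint for each patient randomised and accepts the value nearest week 16 between weeks 12 and 20. Section 7.2 says that "efforts will be made to conduct all evaluations irrespective of whether the participants complete the study treatment regimen or not". FVC is also measured at weeks 4 and 8 (Section 6.8), so those values, or baseline, are what LOCF would carry.

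**The concern.** The conservatism argument imagines the drop-out staying and continuing to benefit. The follow-up commitment in Section 7.2 points to a different quantity: FVC at week 16 whether or not treatment was completed. For a CLEAR patient who leaves and has no value in the window, that is likely to be an off-drug value. LOCF substitutes a week 4 or week 8 on-drug value. The section considers only the directions in which LOCF errs against CLEAR, and never a gain that fades after leaving.

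The documents make that case possible, though they do not establish it. Participants must show evidence of progression (Section 4.5.1). Section 1.4 cites FVC improvement among patients completing an 8-week regimen, so there may be an early gain to carry. In Phase I, with 30% drop-out, "patients with advanced disease accounted for the majority of the study withdrawals" (Section 7.3).

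What is at stake is how the sensitivity result is read. An estimate labelled conservative will be taken as a lower bound, and LOCF need not be one.

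**Working it through.** **Plan's own figure.** Section 7.3 states "We need a sample size of 51 completed participants per arm to have 90% power to detect a 5% difference", with 5 points on CLEAR, 0 on placebo, and "we obtained the SD of 7.7 for the primary endpoint". The test is a t-test (Section 7.1.1). Alpha is not stated; I assume 0.05 two-sided. The normal approximation is 2 × (1.960 + 1.282)² × 7.7² / 5² = 49.8, so 50. The noncentral t gives 51 per arm (power 0.901). Inflating, 51 / 0.8 = 63.75, so 64. The plan's numbers reproduce.

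**Bias of LOCF against the effect in all randomised patients.** Let dC and dP be the fractions with no usable week 16 FVC, g and gP the carried changes, and t and tP the true week 16 changes in those patients:

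bias = dC × (g − t) − dP × (gP − tP)

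From the documents: completers at 5 (CLEAR) and 0 (placebo), and 20% drop-out. Assumed: equal drop-out by arm, its timing, the shape of the gain and the off-drug course. With placebo flat the second term is zero, the completers' estimate is 5.0, LOCF gives 0.8 × 5 + 0.2 × g, and the truth is 0.8 × 5 + 0.2 × t.

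| Scenario | g | t | Completers | LOCF | All randomised | Bias |
|---|---|---|---|---|---|---|
| Linear gain, lost after week 8, back to baseline | 2.5 | 0 | 5.0 | 4.5 | 4.0 | +0.5 |
| Full gain by week 8, then back to baseline | 5 | 0 | 5.0 | 5.0 | 4.0 | +1.0 |
| All leave before week 4, back to baseline | 0 | 0 | 5.0 | 4.0 | 4.0 | 0 |
| Linear gain, drop-outs would have reached target | 2.5 | 5 | 5.0 | 4.5 | 5.0 | −0.5 |

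Rows 1 and 4 give the same LOCF estimate, 4.5. The method cannot tell the case in which it is conservative from the case in which it is not.

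**Variations.**
- 30% missing on CLEAR (the Phase I rate), placebo flat: 0.3 × 2.5 = +0.75 and 0.3 × 5 = +1.5.
- Placebo falling 2 points by week 16 and 1 by week 8: the second term subtracts 0.2 × (−1 + 2) = 0.2. Row 1 becomes +0.3 and row 4 becomes −0.7. If CLEAR drop-outs also fall to −2, the bias is 0.2 × 4.5 − 0.2 = +0.7.

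**Simulation** (8,000 trials, 64 per arm, 13 missing per arm, SD 7.7, assumed AR(1) correlation 0.6). Row 1: LOCF 4.48 against a true 3.97, 95% interval coverage 93.7%. Row 2: 5.00 against 3.98, coverage 88.9%. Row 2 with 19 CLEAR and 6 placebo missing: bias +1.49, coverage 80.6%.

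**Standard error.** With imputed values counted as observed, 7.7 × √(2/64) = 1.36. For 51 completers, 7.7 × √(2/51) = 1.52. The first is about 11% smaller because imputation uncertainty is left out. In the row 1 simulation the mean reported SE (1.364) matched the empirical SD of the LOCF estimate (1.356).

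**The case against.** The other side has a good deal right, and most of it limits the point.

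- **LOCF is optional, secondary and not alone.** It sits beside a committed multiple imputation and a second option in the same sentence, and it cannot change the primary result. This stands and lowers the severity.
- **Stopping drug is not the same as missing FVC.** Sections 5.1, 7.2 and 12.1 continue data collection after drug is stopped, Section 5.7 asks at least for follow-up spirometry, and the window is eight weeks wide. LOCF touches only patients with no usable value.
- **LOCF usually falls below the completers' estimate.** In these scenarios it never materially exceeded it. A reader might infer that LOCF would endorse a false positive, but this is not shown: it moves towards zero relative to the primary analysis or leaves it unchanged. What remains is that sitting below 5.0 does not put it at or below 4.0.
- **Type I error.** A reader might also infer inflation. With no drug effect at any visit, simulated rejection was 4.9% to 5.3%. Rates of 8% to 14% can be produced only by making CLEAR completers reverse from +2.5 at week 8 to −2 at week 16 while on treatment. Nothing in the documents supports that.
- **Standard error.** It is tempting to say the SE is too small. As the sampling SE of the LOCF statistic it is not; the poor coverage comes from bias.
- **Ignorability test.** No stated choice of method depends on its result. The remaining problem is only that it promises something the observed data cannot deliver.

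**Conclusion.** The claim that LOCF is conservative should not stand. Its direction depends on whether the carried CLEAR change exceeds what those patients would show at week 16, and the plan considers only the favourable answer. With 20% missing per arm and placebo flat, the bias runs from about −0.5 to +1.0 points against a 5-point target. It is +0.5 for a half-size week 8 gain that is lost and 0 when all leave before week 4 and return to baseline. The design's 0% placebo change also means that, on its own assumption, placebo worsening adds no conservatism.

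These sizes rest on assumed drop-out timing, gain shape and off-drug course, none of which the documents give. The finding is that LOCF can favour CLEAR, not that it will. Severity is low to moderate: the primary analysis and sample size are unchanged.

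**What to change.** In Section 7.1.4 Missing Data Analyses:

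1. Remove LOCF and the statement that it is conservative.
2. State that MAR and MNAR cannot be told apart by a test on the observed data. Describing how missingness relates to covariates can remain.
3. Keep the planned multiple imputation and specify that its model includes treatment arm and week 4 and week 8 FVC.
4. Replace the optional wording with two committed sensitivity analyses: (a) reference-based multiple imputation, with CLEAR drop-outs imputed from the placebo trajectory; and (b) a delta-adjusted tipping-point analysis that worsens imputed CLEAR values until significance is lost, reporting the shift needed.

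Under the flat-placebo assumption, a jump-to-reference form of (a) would centre the missing CLEAR patients at 0 and return 0.8 × 5 + 0.2 × 0 = 4.0 in row 1. It would be too pessimistic in row 4, which is why (b) is wanted as well.

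The cost is SAP wording, modest programming, and a sensitivity result that may look less favourable to CLEAR.
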